TITLE: Use of tolvaptan, a vasopressin antagonist, to increase urine dilution and reduce cystine urolithiasis among patients with homozygous cystinuria: a pilot investigation

NCT02538016

Latest IRB Approval Date: 9/23/2019

A. Specific Aims/Objectives

The goal of this research project is to establish that in short-term use, tolvaptan is a safe and potentially effective new therapy for cystinuria, by conducting a short-term pilot study of the safety and tolerability of this drug, and assess impact on urinary stone risk parameters, among adolescent and young adult patients with clinical cystinuria.

Specific Aim 1) To characterize the short-term safety profile of tolvaptan therapy in adolescent patients with cystinuria.

Hypothesis 1a: Tolvaptan will be well tolerated with low adverse effects, minimal disruption of serum electrolytes, and no detectable alterations in blood pressure and other cardiovascular parameters

Specific Aim 2) To characterize the short-term effect of tolvaptan on urinary risk factors for urolithiasis in adolescent patients with cystinuria.

Hypothesis 2a: Tolvaptan therapy will result in >25% increased urine output, decrease in urinary osmolality of >25%, and increase in urinary cystine capacity of >25%

B. Background and Significance

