Cystinuria pathophysiology. Cystinuria is a rare disorder of amino acid metabolism that leads to high levels of cystine in the urine. (Cystine is a dimeric amino acid formed from two cysteine amino acid residues linked by a disulfide bond.) Patients with cystinuria have mutations in one of two genes (SLC3A1 and SLC7A9) that encode subunits of the amino acid transporters that are responsible for reabsorbing filtered cystine and dibasic amino acids (ornithine, lysine, and arginine) from the lumen of the proximal renal tubule into the tubular cells. Although in normal individuals virtually 100% of the filtered load of amino acids is reabsorbed from the proximal tubule, homozygotes (and some heterozygotes, depending on the mutation) are unable to reabsorb these amino acids. These individuals therefore excrete large amounts of these amino acids into the urine. As cystine is relatively insoluble in urine, it precipitates into crystals and dense stone stones, resulting in clinical urolithiasis. The condition is rare; homozygous cystinuria occurs in about 1/15,000 persons in the United States (~20,000 affected individuals nationwide)(1). Age at presentation is variable, but significant numbers of patients present during childhood or adolescence with clinical stone disease, with over 80% presenting before age 20(2).

Urolithiasis in patients with cystinuria is a difficult problem to manage. Stones tend to be large and recurrent, form rapidly, and require repeated surgical treatments. This often has devastating effects on renal function over the long-term, such increased probability of nephrectomy, high incidence of decreased GFR, and progression (in some rare cases) to end-stage renal disease(2, 3).

Contemporary cystinuria management. Metabolic strategies for preventing cystine stones focus on increasing solubility of cystine in the urine, through dilution, alkalinization, or chelation.

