Tolvaptan in cystinuria. We have not yet treated any pediatric cystinuria patients with tolvaptan. We believe that, given the uncertainty regarding safety and efficacy of this treatment in this population, the treatment should be administered within the framework of a research study with careful monitoring. The only reported instance of using tolvaptan for treatment of cystinuria was reported by de Boer et al. in two adult patients(30). Each of these patients was treated for 5 days with tolvaptan; both exhibited a significant increase in urine output, decrease in urine cystine concentration, and a minor increase in plasma osmolality. Both patients experience minor thirst symptoms but otherwise tolerated treatment well. The authors concluded that this was a promising potential treatment for cystinuria (and in fact any chronic lithogenic condition), and that further studies of this agent were warranted.

D. Design and Methods

(1) Study Design

We will conduct a single-arm, unblinded, short-term prospective evaluation of tolvaptan in patients with cystinuria. The goal will be to obtain safety and short-term effectiveness data on Tolvaptan in adolescent to young adult patients, to demonstrate tolerability and favorable impact on urinary parameters associated with cystine urolithiasis risk.

(2) Patient Selection and Inclusion/Exclusion Criteria

Sample population

For this pilot study 16 patients with cystinuria will be recruited for 8 complete participants. Subjects will be recruited from our existing database of cystinuria patients seen in the

Boston Children's Hospital Pediatric Kidney Stone Clinic, and from new patients diagnosed during the research period who present to Boston Children's Hospital. We will also consider recruitment through advertising in other outlets e.g. International Cystinuria Foundation, Rare Kidney Stone Consortium.

Inclusion criteria:

Males and females age 12 – 25 years

Weight \geq 25kg

Confirmed cystinuria via:

Documented cystine stones (stone >75% cystine on chemical analysis),

Cystine crystals in urine (pathognomonic hexagonal crystals),

Urinary cystine levels greater than 250 mg/L or

Genetic screening.

Estimated GFR greater than 80 ml/min/1.73 m²

Exclusion criteria:

Concurrent non-renal disease that might increase risk of complications due to aquaresis.

Liver or biliary disease (chronic or acute)

Malabsorption syndrome or other gastrointestinal condition that may interfere with response to therapy

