Non-cutaneous malignancy within last 5 years

History of adverse reaction or allergy to Tolvaptan or other arginine vasopressin V₂-receptor antagonists

Positive pregnancy test

Currently breastfeeding

Inability or unwillingness to consent/assent

(3) Description of Study Treatments or Exposures/Predictors

Starting at between 10AM and 2PM on Day 1, Tolvaptan will be administered orally. See dose chart below:

T-CUPS:

Tolvaptan use in Cystinuria and Urolithiasis: A Pilot Study

DOSING SCHEDULE by WEIGHT

Weight (kg)	Day 1-4	Day 5-8
12.5 kg -37.49 kg (mean=25kg) For illustration: We will not recruit anyone weighing less than 25kg.	7.5mg (.6mg/kg - .2mg/kg)	15mg (1.2mg/kg - .4mg/kg)
37.5kg-62.49kg (mean =50kg)	15.0 mg (.4mg/kg - .24 mg/kg)	30mg (.8mg/kg - .48mg/kg)
62.5 kg -87.49kg (mean 75kg)	22.5 mg (.36mg/kg - .26mg/kg)	45.0mg (.72mg/kg - .52mg/kg)
87.5 kg – 112.49kg (mean 100kg)	30.0 mg (.34mg/kg - .27mg/kg)	60.0mg (.68mg/kg - .54mg/kg)
112.5kg – 137.5kg (mean 125kg)	37.5 mg (.33 mg/kg - .27mg/kg)	60.0mg (.66mg/kg - .54mg/kg)

This daily dose will continue for a total of 4 doses, through Day 4. On Day 5, the dose will be increased per chart, up to a maximum dose of 60 mg. If tolerated, the higher dose will be continued for a total of 4 doses through Day 8. No drug will be given on day 9 or 10.

Tolvaptan is produced commercially as 15 mg triangular tablets and 30 mg round tablets.

Patients currently on chelation therapy will NOT discontinue these medications during the study period.

(4) Definition of Primary and Secondary Outcomes/Endpoints

The primary outcome will be urinary cystine levels as measured by cystine capacity (Litholink Corp; mg/L). Four 24-hour urine samples will be obtained during the study: one at baseline 3-6 days prior to the measurement, one on day 3-4 of the dosing period, one on day 7-8 of the dosing period, and one 3-6 days after the washout period. Each 24 hour urine sample will be sent individually for analysis by Litholink Corp, which performs the cystine assays.

Secondary outcomes will include daily urine output and urine osmolality. Additional data points to be collected include serum sodium and other electrolyte levels, serum osmolality, plasma AVP concentration, and urinary electrolytes and osmolality. Urinary symptoms will be measured with the AUA symptom score.

(5) Data Collection Methods, Assessments, Interventions and Schedule (what assessments performed, how often)

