All information will be collected and reported onto a paper case report forms (CRFs), which will later be entered into REDCap. 24 hour urines and clinical (vital signs, weights, fluid intake and output, thirst and dry mouth) and laboratory data (urine cultures/analysis, serum electrolytes and liver function tests) will be collected throughout the duration of the patient's participation in the research study. The following table indicates the procedures that will be done each day the patient is involved with the research study:

3-6 days before	Day 0	Day 1	Day 2	Day 3
-----------------	-------	-------	-------	-------

Day 0				
24 hour urine collection.	CTSU-Outpt. Physical exam. Blood sample. Urine sample.	CTSU – admitted. Tolvaptan given orally. Urine sample.	CTSU – discharged Tolvaptan given orally. Blood sample. Urine Sample	CTSU – outpatient. Tolvaptan given orally. 24 hour urine collection.

Day 4	Day 5	Day 6	Day 7	Day 8
CTSU – outpatient. Tolvaptan given orally. Blood sample.	CTSU – admitted. Tolvaptan given orally. Urine sample.	CTSU – discharged. Tolvaptan given orally. Blood sample. Urine Sample	CTSU – outpatient. Tolvaptan given orally. 24 hour urine collection.	CTSU – outpatient. Tolvaptan given orally. Blood sample.

Day 9	Day 10	3-6 days after Day 10
CTSU – outpatient. No medication given. .Urine sample	CTSU – outpatient. No medication given. Blood sample.	24 hour urine collection.

(6) Study Timeline (as applicable)

The study will be conducted through the Clinical and Translational Study Unit at Boston Children’s Hospital. The treatment period will for 8 days. Subjects will be spend two 24-hour periods under inpatient observation; the remainder of the period will be under outpatient observation, with daily visits to the CTSU. The day prior to the treatment period (Day 0) will be used to obtain baseline clinical and laboratory data. Study drug will be administered starting on Day 1 through Day 8, with a 2 day washout period on days 9 and 10. Patients will be monitored during the period with 24-hour urine collection for cystine stone risk profile, daily weights, vital signs, blood draws, fluid intake and output, and assessment of subjective outcomes.

E. Adverse Event Criteria and Reporting Procedures

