Subjects will be monitored for drug tolerability and safety. Patients will be observed in the inpatient CTSU setting for 24 hours after the initial dose (Day 1) and also for 24 hours after the increased dose (Day 5). During each of these 24 hour periods, subjects will undergo around the clock monitoring of vital signs and daily input and outputs.. On Day 2-4 and Day 6-8 subjects will be monitored on an outpatient basis, coming in each day to the CTSU. At each outpatient visit vital signs will be checked. Serum Electrolytes will be checked on days 0, 2, 4, 6, 8,and 10. Liver function tests will be obtained at baseline, Day 4, and Day 8, and Day 10. Thirst and dry mouth will be assessed daily with visual analog scales. (31-33).

Criteria for cessation of treatment will include abnormal serum sodium (>5 mmol/L above or below normal range), potassium (>0.2 mmol/L above or below normal range), or CO₂ (>2 mmol/L above or below normal range). Other criteria will include unstable vital signs (e.g. tachycardia, hypotension), intolerable subjective symptoms of thirst or voiding symptoms, or other symptoms subjectively attributed to the medication.

Subjects that experience adverse reaction at the higher dose level will be reduced to the lower dose level; if adverse effects persist at the lower dose level, the study drug will be discontinued.

For other potential adverse events not listed above, the investigators will decide on a case-by-case basis whether treatment should be continued, taking the subject's short-term and long-term health and safety as the primary factor for consideration.

F. Data Management Methods

Clinical and laboratory data will be maintained in a secure REDCap database.

G. Quality Control Method

Trained research personnel will be collecting data and entering it into REDCap. There also will be data checks within the REDCap system.

H. Data Analysis Plan

In this pilot study, the primary analysis will be description of the change from baseline during treatment of cystine stone risk profile. This will be demonstrated graphically. With respect to the primary endpoint, differences in cystine capacity between baseline and low-dose treatment phase, and between baseline and the high-dose treatment phases, will be compared with paired t-tests. Data regarding thirst and dry mouth will also be recorded and demonstrated graphically.

I. Statistical Power and Sample Considerations

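### The plan sets an eGFR limit for entry but does not commit to measuring or reporting kidney function after entry, so Aim 1 could conclude on safety without an on-drug kidney-function result

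*Combined protocol and SAP*

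**What the plan says.** **Entry.** The inclusion criteria in D(2) require "Estimated GFR greater than 80 ml/min/1.73" m². No equation for the estimate is given.

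**Background.** Section B says of recurrent cystine stones and their surgery: "This often has devastating effects on renal function over the long-term". Among the consequences it lists "increased probability of nephrectomy, high incidence of decreased GFR".

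**Aim 1.** Hypothesis 1a in Section A expects few adverse effects, "minimal disruption of serum electrolytes, and no detectable alterations in blood pressure and other cardiovascular parameters". Kidney function is not among the domains named.

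**Measurements after entry.**
- D(4): "Additional data points to be collected include serum sodium and other electrolyte levels, serum osmolality, plasma AVP concentration, and urinary electrolytes and osmolality".
- D(5): "laboratory data (urine cultures/analysis, serum electrolytes and liver function tests", together with vital signs, weights, fluid balance, thirst and dry mouth. The day-by-day table says only that a blood sample is taken and names no analyte.
- Section E: "Serum Electrolytes will be checked on days 0, 2, 4, 6, 8,and 10". Liver tests are at baseline and Days 4, 8 and 10. The laboratory criteria for stopping concern sodium, potassium and CO₂.

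**Analysis.** Section I summarises electrolyte and cardiovascular measures as the proportion of subjects with at least one clinically abnormal value. A parenthesis extends this to every serum chemistry value, without a list.

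**The concern.** Aim 1 is to characterise short-term safety. The drug acts on the kidney, and Section B describes loss of kidney function as a main long-term harm of the disease. The plan treats kidney function as important enough to exclude people on, then does not say that it will be looked at again.

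Two things are at stake. First, a safety statement could be issued with no on-drug kidney-function result behind it, and a value that was never measured cannot be recovered afterwards. Second, if creatinine happens to be on the chemistry panel, the planned summary asks only whether a value is outside the normal range. That is a weak way to look for change in people selected for having good function. A subject could lose a good deal of eGFR, or fall to the plan's own entry limit, without the report having to show it.

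**Working it through.** The plan gives no figure on this point, so there is none to reproduce. The check has three steps.

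**1. Text.** Creatinine and BUN appear nowhere in the document. GFR appears twice: as a long-term harm in Section B and as an entry criterion in D(2). Neither is a measurement after entry. Blood is scheduled on six days (0, 2, 4, 6, 8 and 10). Days 2 and 4 fall in the lower-dose phase, Days 6 and 8 in the higher-dose phase, and Day 10 is washout. The samples for a within-subject comparison therefore already exist.

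**2. What the Section I summary would show if creatinine were on the panel.** Take an illustrative subject whose eGFR goes from 125 to 85 ml/min/1.73 m². The relative fall is (125 − 85)/125 = 32%. The subject is still above 80. If the laboratory's range contains both creatinine values (an assumption, since no range is given), the subject counts as having no outlier. A count with no events would also say little: with 0 of n subjects, the one-sided 95% upper bound on the true rate is 1 − 0.05^(1/n), which is 31.2% for n = 8 and 17.1% for n = 16.

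**3. What a change-from-Day-0 summary would show.** The half-width of the 95% CI for a mean paired change is t(0.975, n − 1) × SD/√n. The SD of within-subject percent change in eGFR is not in the documents, so I assume 8, 10 and 15 points. D(2) plans 8 completers from 16 recruited. For n = 8, t = 2.365 and √8 = 2.828. For n = 16, t = 2.131 and √16 = 4.

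| Assumed SD (points) | Half-width, n = 8 | Half-width, n = 16 | Power for a true 10-point fall, n = 8 |
|---|---|---|---|
| 8 | 2.365 × 8/2.828 = 6.7 | 2.131 × 8/4 = 4.3 | 86% |
| 10 | 2.365 × 10/2.828 = 8.4 | 2.131 × 10/4 = 5.3 | 68% |
| 15 | 2.365 × 15/2.828 = 12.5 | 2.131 × 15/4 = 8.0 | 37% |

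Power is for a two-sided 5% paired t-test (noncentral t, 7 degrees of freedom, noncentrality 10√8/SD). With 8 subjects the half-width is below 10 points at SDs of 8 and 10 but not at 15, and only at SD 8 does power exceed 80%. The n = 16 column is a best case, in which everyone recruited is dosed and contributes a change.

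**The case against.** **Silence is not absence.** The D(4) list is introduced as open, Section I's reference to serum chemistry is wider than electrolytes, and the schedule table names no analyte on any day, so it does not name sodium either. The closing note adds that, for an IND or IDE submission, this document alone is not the full protocol; whether that applies here is not stated. This objection stands as a limit on the claim. A reader might infer that creatinine will not be measured, or that the trial must end with no estimate of the effect on GFR. The documents show only that the plan does not commit to either the measurement or the report.

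**Safety is monitored widely.** A reader might also infer that the safety conclusion would rest on electrolytes, vital signs and liver tests alone. It would not. The plan also collects serum osmolality, AVP, weights, fluid intake and output, urine tests, symptom scores and classified adverse effects. None of these, however, is a committed measure of kidney function.

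**The renal harm in Section B is long-term and due to stones.** Entrants have eGFR above 80 and receive drug for eight days, the tolvaptan harms that Section B reports are aquaresis effects and raised liver enzymes, and the monitoring matches Hypothesis 1a. This is fair. Section B is not evidence that tolvaptan lowers GFR in the short term, and entrants should not be described as having impaired function. But Section A sets out to establish short-term safety, D(1) makes safety data a goal, and Section C says that this group has not yet treated a pediatric cystinuria patient with the drug. Repeated liver tests show that organ function is within scope. Normal function at entry is also where an in-or-out-of-range count is least able to show a change.

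**Conclusion.** The point holds as a gap in commitment. Kidney function is an entry criterion, no section commits to measuring or reporting it afterwards, and the one analysis that might pick it up would miss a fall that stays within range. Aim 1's conclusion could therefore be drawn without a committed on-drug kidney-function result.

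The textual finding needs no assumption. The precision figures rest on assumed SDs of 8 to 15 points. With 8 subjects the half-width is 6.7 to 12.5 points, so it would be too strong to say that a mean fall of about 10% could in general be seen or excluded; at an SD of 15 it could not. The gain is a per-subject record and a rough mean change, not proof that renal effects are absent. The change is worth making because it is cheap and an unmeasured value cannot be recovered later, but it does not put the trial's primary outcome in doubt.

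**What to change.** 1. In D(4) and Section E, name serum creatinine among the analytes on the blood already drawn on Days 0, 2, 4, 6, 8 and 10, and list eGFR as an Aim 1 safety outcome.
2. Name one eGFR equation suitable for ages 12 to 25, and use it both for the entry criterion and on study. At present none is named, so entry and follow-up values might not be comparable.
3. In Section I, report for every subject dosed, not only completers, the absolute and percent change in eGFR from Day 0 at each dose level and at Day 10. Give individual values, a mean with 95% CI, and the number of subjects at or below 80 at either dose. Assign each value to the dose actually taken, since Section E provides for dose reduction, and state how many subjects contribute to each mean.
4. Describe the result as an estimate with limited precision, without a pass or fail threshold.

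**Cost.** One added analyte on existing samples (none if it is already on the panel) and one safety table. No new visit, blood draw or patient is needed. Any clinical action on a result stays with the investigators.

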Hydration therapy is the underlying foundation of all therapy for cystinuria. Hydration therapy is based on an idea that, given a relatively constant amount of cystine being excreted in the urine each day, adequate hydration will result in dilution of the fixed cystine load to a concentration below that at which crystallization typically occurs. Target concentrations are usually set at about 250 mg/L, as stone formation rates increase significantly at concentrations above this. While simple in concept, and although there is longstanding evidence that hyperhydration can be effective in reducing stone recurrence(4), in practice adequate oral hydration is difficult to achieve for many patients. The target cystine concentration requires a urine volume of over 3 L per day, which in turn requires fluid intake of greater than 3.5-4 L per day. Many patients find that they cannot sustain this level of intake voluntarily.

A complementary strategy for reducing cystine crystallization is to chemically alter the solubility of cystine. Below pH of 7.0, the solubility of cystine is relatively constant at about 250 mg/L. However, as pH rises above 7.0, solubility increases to about 500 mg/L at 7.5(1). Thus, alkalinization has been used to increase urinary pH to a range that permits significantly more cystine in solution in the urine, regardless of volume. Potassium citrate is the agent most commonly used for this purpose, is well tolerated, and avoids the potential negative effects of using the sodium salts, as sodium intake appears to increase cystine excretion(1, 5).

Dietary modification to reduce cystine intake is attractive, in theory. Reduction in dietary animal protein intake has been found to reduce the excretion of cystine and other amino acids(6). Such reduction is also associated with increase in urine pH. However, exogenous protein is not the only source of cystine in the body; the amino acid is produced as part of metabolic processes. Thus, the potential impact of reduced intake is blunted

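### Section H measures both dose effects against one pre-visit urine and leaves the post-washout urine and the recorded fluid intake unused

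*Combined protocol and SAP*

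**What the plan says.** Section D(1) describes a "single-arm, unblinded, short-term prospective evaluation of tolvaptan in patients with cystinuria". Time and setting are therefore controlled only by comparing each subject with himself or herself.

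The D(5) schedule has four 24-hour urines. The baseline is collected 3-6 days before Day 0, and Day 0 is the first scheduled visit to the Clinical and Translational Study Unit (CTSU). The low-dose urine is on Day 3, after the admission of Days 1-2. The high-dose urine is on Day 7, after the admission of Days 5-6. D(4) lists the last two as "one on day 7-8 of the dosing period, and one 3-6 days after the washout period"; the schedule places the final one 3-6 days after Day 10. Apart from the two admissions, D(6) says "the remainder of the period will be under outpatient observation, with daily visits to the CTSU".

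D(5) also provides for collecting "24 hour urines and clinical (vital signs, weights, fluid intake and output, thirst and dry mouth" ratings, among other data, throughout participation.

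In Section H the primary analysis is a graphical description of change from baseline during treatment. The only formal test is specified as follows: "differences in cystine capacity between baseline and low-dose treatment phase, and between baseline and the high-dose treatment phases, will be compared with paired t-tests". Neither the post-washout urine nor fluid intake appears there.

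**The concern.** The reference urine and the on-drug urines differ in more than drug. The baseline is collected before any scheduled CTSU contact. The others are collected in the middle of daily visits, shortly after a 24-hour stay with inputs and outputs monitored. The available text gives no fluid instruction for any of these periods.

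Drinking matters here because Section B says that "adequate hydration will result in dilution of the fixed cystine load to a concentration below that at which crystallization typically occurs". More drinking alone would move urine output, osmolality and cystine capacity in the direction of Hypothesis 2a. Drinking driven by drug-induced thirst belongs to the drug effect; drinking prompted by attendance does not. Any steady change over the study weeks would also be counted as drug effect.

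Both planned tests use the same baseline urine as their only reference. The one repeat off-drug urine that could show whether the reference had moved is already scheduled, but no planned comparison uses it.

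**Working it through.** The plan gives no figure on this point to reproduce. D(2) states 16 recruited for 8 completers, without a power calculation.

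**Timing.** Inputs are collection start days from the D(5) schedule: baseline Day -6 to -3; low dose Day 3; high dose Day 7; post-washout 10+3 to 10+6 = Day 13 to 16. If a measure drifts by d per day, the bias in a comparison is d x (on-drug day - reference day).

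| Comparison | Low dose (Day 3) | High dose (Day 7) |
|---|---|---|
| Minus baseline | 3+3 to 3+6 = +6 to +9 days | 7+3 to 7+6 = +10 to +13 days |
| Minus post-washout | 3-13 to 3-16 = -10 to -13 days | 7-13 to 7-16 = -6 to -9 days |
| Minus mean of both off-drug urines | 3-3.5 to 3-6.5 = -0.5 to -3.5 days | 7-3.5 to 7-6.5 = +0.5 to +3.5 days |

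The last row uses the midpoint of the two off-drug urines, from (-6+13)/2 = 3.5 to (-3+16)/2 = 6.5. Linear drift enters the two single-reference comparisons with opposite sign. Against the mean of both, at most 3.5 days of it remain at either dose. The post-washout urine is 13-8 = 5 to 16-8 = 8 days after the last dose on Day 8.

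**Drinking.** The documents give no baseline output, so I assume 2.0 L/day (range 1.5-3.0) and that all extra intake appears as urine.

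- A 25% rise in output needs 0.25 x V: 0.5 L/day (0.375-0.75).
- A 25% fall in osmolality at fixed solute needs V x (1/0.75 - 1): 0.67 L/day (0.5-1.0).
- For capacity, Section B's 250 mg/L and 3 L/day imply a load of about 750 mg/day. With constant solubility of 250 mg/L, capacity is roughly 250 - 750/V. An extra 0.5 L/day moves it from -125 to -50 mg/L at a 2.0 L baseline, a shift of 75 mg/L. The shift is 125 mg/L from 1.5 L and 36 mg/L from 3.0 L.

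The capacity model ignores chelators, which D(3) keeps in place: "Patients currently on chelation therapy will NOT discontinue these medications during the study period". These figures show what would suffice, not what is likely. They say nothing about the 25% capacity criterion, because a percentage change from a negative or zero baseline has no clear meaning.

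**Precision.** With 8 completers, the 95% CI half-width for a paired mean is t(0.975, 7)/sqrt(8) = 2.365/2.828 = 0.84 SD of the paired differences.

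**The case against.** The strongest reply is that this is a small pilot with a mainly descriptive primary analysis and an openly stated single arm. No drift rate is known, the litre figures rest on an assumed baseline output, and nothing shows that visits change drinking. All of that stands, and it limits the weight of the point. A reader might infer that the planned tests would be significant through drinking alone. The documents do not support that: they give neither the SD of change in capacity nor any visit-related change in intake.

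A reader might also suspect regression to the mean. The documents do not support that either. Subjects are not selected on the baseline urine, and urinary cystine above 250 mg/L is only one of four routes to confirming the diagnosis. Positive capacity is favourable, so a chance high baseline capacity would hide a benefit.

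The two dose phases have similar supervision, so a larger change at the higher dose would give some reassurance. It is partial: dose order is fixed, the two urines are 4 days apart, and "Subjects that experience adverse reaction at the higher dose level will be reduced to the lower dose level". Serum sodium on Days 4 and 8 also bears on drug versus drinking, since Section B expects aquaresis to raise it. Section I, however, plans only proportions of subjects with abnormal values.

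Missing fluid instructions are weak evidence of a gap. Consent pages are not in the available text, and an instruction may exist there. The available text also says that intake is recorded throughout participation. What is unclear is whether that covers the two collections outside the visit period, because D(6) ties monitoring to the study period.

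Finally, the post-washout urine comes after both drug and visits have ended, so it cannot isolate attendance-driven drinking. That is correct, and the added comparisons should not be presented as doing so.

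**Conclusion.** The point holds as a limited one. Section H relies on a single pre-visit reference and omits a scheduled off-drug urine and recorded intake, so drift or a change in drinking could contribute to the change credited to tolvaptan. Neither is demonstrated. The firm figures are calendar ones from the schedule's start days: linear drift over 6-9 days (low dose) and 10-13 days (high dose) enters the planned comparisons, against at most 3.5 days when both off-drug urines are used. They bound exposure to drift and do not estimate its size. The drinking figures depend on the assumed baseline output.

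It would go too far to conclude that the expected effect is an artefact, or that using the fourth urine would rule out attendance-driven drinking. Severity: consider.

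**What to change.** In Section H, for each dose, report the paired on-drug minus post-washout difference (mean, 95% CI) beside the planned baseline comparison, and also the difference from the mean of the two off-drug urines. Plot each subject's cystine capacity, urine output, osmolality and fluid intake at all four collections. Do not adjust for intake, because drug-induced thirst is part of the effect. State that these comparisons check drift and reversibility but cannot separate the end of drug from the end of visits.

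In D(5), give one unchanged instruction from before the baseline collection through the post-washout collection: usual fluid advice, drink to thirst, no upper limit. Confirm that intake is recorded at the two collections outside the visit period.

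The cost is a sentence of instruction, a one-day intake record for those two collections where it is not already kept, a few more paired differences and extra panels in the planned graphs. No visit, sample or assay is added. The downsides are that baseline output may rise, which would make the observed change smaller, and that intervals of 0.84 SD either side keep the added comparisons descriptive.
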